3.1 Current Study Status

Investigators should refer to the COG website to determine if the study is currently open for accrual. If the study is listed as active, investigators should then access the Studies Requiring Reservations page to ensure that a reservation for the study is available. To access the Studies Requiring Reservations page:

1. Log in to <https://open.ctsu.org/open/>
2. Click the **Slot Reservation** Tab. *The Site Patient page opens.*
3. Click the **Report** Tab. *The Slot Reservation Report opens. Available Slots are detailed per study strata.*

3.2 IRB Approval

NCI Pediatric CIRB approval or local IRB approval of this study must be obtained by a site prior to enrolling patients. Sites must submit CIRB/IRB approvals to the NCI's Cancer Trials Support Unit (CTSU) Regulatory Office and allow 3 business days for processing. The CTSU IRB Certification Form may be submitted in lieu of the signed IRB approval letter. All CTSU forms can be located on the CTSU web page (www.ctsu.org). Any other regulatory documents needed for access to the study enrollment screens will be listed for the study on the CTSU Member's Website under the Regulatory Tab.

Sites participating on the NCI CIRB initiative and accepting CIRB approval for the study are not required to submit separate IRB approval documentation to the CTSU Regulatory Office for initial, continuing or amendment review. This information will be provided to the CTSU Regulatory Office from the CIRB at the time the site's Signatory Institution accepts the CIRB approval. The Signatory site may be contacted by the CTSU Regulatory Office or asked to complete information verifying the participating institutions on the study.

Submitting Regulatory Documents:

Submit required forms and documents to the CTSU Regulatory Office via the Regulatory Submission Portal, where they will be entered and tracked in the CTSU RSS.

THIS PROTOCOL IS FOR RESEARCH PURPOSES ONLY, SEE PAGE 1 FOR USAGE POLICY

Regulatory Submission Portal: www.ctsu.org (members' area) → Regulatory Tab
→ Regulatory Submission

When applicable, original documents should be mailed to:

CTSU Regulatory Office
[name]
[name]

Institutions with patients waiting that are unable to use the Portal should alert the CTSU Regulatory Office immediately at [name] in order to receive further instruction and support. For general (non-regulatory) questions, call the CTSU General Helpdesk at [name] or contact CTSU by email at [contact].

Study centers can check the status of their registration packets by accessing the Site Registration Status page on the CTSU Member's Website under the Regulatory Tab. (Note: Sites will not receive formal notification of regulatory approval from the CTSU Regulatory Office.)

3.3 **Patient Registration**

Prior to enrollment on study, patients must be assigned a COG patient ID number. This number is obtained via the COG Registry in the OPEN system once authorization for the release of protected health information (PHI) has been obtained.

3.4 **Reservation and Contact Requirements**

Before enrolling a patient on study, a reservation must be made through the OPEN website and the Study Chair or Vice Chair should be notified. (The patient will need a COG patient ID number in order to obtain a reservation). Patients must be enrolled within 7 calendar days of making a reservation.

Reservations may be obtained 24-hours a day through the OPEN website.

3.5 **Informed Consent/Accent**

The investigational nature and objectives of the trial, the procedures and treatments involved and their attendant risks and discomforts, and potential alternative therapies will be carefully explained to the patient or the patient's parents or guardian if the patient is a child, and a signed informed consent and assent will be obtained according to institutional guidelines.

3.6 **Screening Procedures**

Diagnostic or laboratory studies performed exclusively to determine eligibility for this trial must only be done after obtaining written informed consent. This can be accomplished through one of the following mechanisms: a) the COG screening protocol, b) an IRB-approved institutional screening protocol or c) the study-specific protocol. Documentation of the informed consent for screening will be maintained in the patient's research chart. Studies or procedures that were performed for clinical indications (not exclusively to determine eligibility) may be used for baseline values even if the studies were done before informed consent was obtained.

3.7 **Eligibility Checklist**

Before the patient can be enrolled, the responsible institutional investigator must sign and date the completed eligibility checklist. A signed copy of the checklist will be uploaded

into RAVE immediately following enrollment.

3.8 Institutional Pathology Report

Immediately following enrollment, the institutional pathology report for the diagnosis under which the patient is being enrolled must be uploaded into RAVE. The report must include the associated study number and COG patient registration and accession numbers. Personal identifiers, including the patient's name and initials must be removed from the institutional pathology report prior to submission.

3.9 Study Enrollment

Patients may be enrolled on the study once all eligibility requirements for the study have been met. Patients who give informed consent for the protocol in order to undergo screening for eligibility are not considered enrolled and should not be enrolled until the screening is completed and they are determined to meet all eligibility criteria. Study enrollment is accomplished by going to the CTSU OPEN (Oncology Patient Enrollment Network) <https://open.ctsu.org/open/>. For questions, please contact the COG Study Research Coordinator, or the CTSU OPEN helpdesk at <https://www.ctsu.org/CTSUContact.aspx>. Patients must be enrolled before treatment begins. The date protocol therapy is projected to start must be no later than five (5) calendar days after the date of study enrollment. **Patients must not receive any protocol therapy prior to enrollment.**

3.10 Dose Assignment

The dose level will be assigned via OPEN at the time of study enrollment.

4.0 PATIENT ELIGIBILITY

All clinical and laboratory studies to determine eligibility must be performed within 7 days prior to enrollment unless otherwise indicated. Laboratory values used to assess eligibility must be no older than seven (7) days at the start of therapy. Laboratory tests need **not** be repeated if therapy starts **within** seven (7) days of obtaining labs to assess eligibility. If a post-enrollment lab value is outside the limits of eligibility, or laboratory values are older than 7 days, then the following laboratory evaluations must be re-checked within 48 hours prior to initiating therapy: CBC with differential, bilirubin, ALT (SGPT) and serum creatinine. If the recheck is outside the limits of eligibility, the patient may not receive protocol therapy and will be considered off protocol therapy. Bone marrow biopsy and/or aspirate must be obtained within 14 days prior to start of protocol therapy.

Clarification in timing when counting days: As an example, please note that if the patient's last day of prior therapy is September 1st, and the protocol requires waiting at least 7 days for that type of prior therapy, then that patient cannot be enrolled until September 8th.

Important note: The eligibility criteria listed below are interpreted literally and cannot be waived (per COG policy posted 5/11/01). All clinical and laboratory data required for determining eligibility of a patient enrolled on this trial must be available in the patient's medical or research record which will serve as the source document for verification at the time of audit.

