4.1.5 Organ Function Requirements

4.1.5.1 Adequate Renal Function Defined as:

- Creatinine clearance or radioisotope GFR $\geq 60\text{ml/min}/1.73\text{ m}^2$ or
- A serum creatinine based on age/gender as follows:

Age	Maximum Serum Creatinine (mg/dL)	
	Male	Female

THIS PROTOCOL IS FOR RESEARCH PURPOSES ONLY, SEE PAGE 1 FOR USAGE POLICY

1 month to < 6 months	0.4	0.4
6 months to < 1 year	0.5	0.5
1 to < 2 years	0.6	0.6
2 to < 6 years	0.8	0.8
6 to < 10 years	1	1
10 to < 13 years	1.2	1.2
13 to < 16 years	1.5	1.4
≥ 16 years	1.7	1.4

The threshold creatinine values in this Table were derived from the Schwartz formula for estimating GFR (Schwartz et al. J. Peds, 106:522, 1985) utilizing child length and stature data published by the CDC.

4.1.5.2 Adequate Liver Function Defined as:

- Bilirubin (sum of conjugated + unconjugated) \leq upper limit of normal (ULN) for age.
- Alanine aminotransferase (ALT) and aspartate aminotransferase (AST) $\leq 2.5 \times$ ULN. For the purpose of this study, the ULN for SGPT is 45 U/L.

4.1.5.3 Adequate Cardiac Function Defined As:

- Shortening fraction of $\geq 27\%$ by echocardiogram, or
- Ejection fraction of $\geq 50\%$ by echocardiogram or radionuclide angiogram
- No ventricular or supraventricular arrhythmia on EKG
- Prolonged rate corrected QT (QTc) interval < 500 msec

4.1.5.4 Adequate Pulmonary Function Defined As:

- Pulse oximetry $> 94\%$ on room air if there is clinical indication for determination (e.g. dyspnea at rest)

4.1.5.5 Adequate Coagulation Defined As:

- INR ≤ 1.5

4.1.5.6 Adequate Bone Marrow Function Defined As:

- Hemoglobin > 8.0 g/dL (may receive RBC transfusions)

4.1.6 Informed Consent: All patients and/or their parents or legally authorized representatives must sign a written informed consent. Assent, when appropriate, will be obtained according to institutional guidelines.

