10.0 CRITERIA FOR REMOVAL FROM PROTOCOL THERAPY AND OFF STUDY CRITERIA

10.1 Criteria for Removal from Protocol Therapy

- a) Evidence of treatment failure (See [Section 12.2.5](#)).
- b) Adverse Events requiring removal from protocol therapy (See [Section 6](#)).
- c) Refusal of protocol therapy by patient/parent/guardian
- d) Non-compliance that in the opinion of the investigator does not allow for ongoing participation.
- e) Completion of 2 cycles of therapy.
- f) Physician determines it is not in the patient's best interest.
- g) Repeated eligibility laboratory studies (CBC with differential, bilirubin, ALT (SGPT) or serum creatinine) are outside the parameters required for eligibility prior to the start of MLN4924 (pevonodistat) (See [Section 8.1](#)).
- h) Study is terminated by Sponsor.
- i) Pregnancy

Patients who are removed from protocol therapy during Cycle 1 should continue to have the required observations in [Section 8.1](#) until the originally planned end of the cycle or until all adverse events have resolved per [Section 13.4.4](#), whichever happens LATER. The only exception is with documentation of the patient's withdrawal of consent. Patients who are removed from protocol therapy in subsequent cycles should have the necessary observations to ensure adequate clinical care.

Patients who are off protocol therapy are to be followed until they meet the criteria for Off Study (see below). Ongoing adverse events, or adverse events that emerge after the patient is removed from protocol therapy, but within 30 days of the last dose of investigational agent, must be followed and reported via RAVE and CTEP-AERS (if applicable). Follow-up data will be required unless consent is withdrawn.

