APPENDIX III: TOXICITY-SPECIFIC GRADING**Bilirubin**

Grade 1:	> ULN - \leq 1.5 x ULN
Grade 2:	> 1.5 x ULN – 3.0 x ULN
Grade 3:	> 3.0 x ULN – 10.0 x ULN
Grade 4:	> 10.0 x ULN

ALT: For the purpose of this study, the ULN for SGPT is 45 U/L regardless of baseline.

Grade 1:	> 45 U/L - \leq 135 U/L
Grade 2:	136 U/L – 225 U/L
Grade 3:	226 U/L – 900 U/L
Grade 4:	> 900 U/L

AST: For the purpose of this study, the ULN for SGOT is 50 U/L regardless of baseline.

Grade 1:	> 50 U/L - \leq 150 U/L
Grade 2:	151 U/L – 250 U/L
Grade 3:	251 U/L – 1000 U/L
Grade 4:	> 1000 U/L

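### The pre-treatment laboratory recheck in 4.0 and 8.1, and the matching rule in 10.1(g), omit AST and INR, although both are laboratory eligibility limits

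*Combined protocol and SAP*

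**What the plan says.** Section 4.0, repeated in 8.1, contains three linked statements.

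- Laboratory values used for eligibility may be at most 7 days old when therapy starts.
- If any post-enrollment value is out of limits, or values are older than that, these tests are repeated within 48 hours before therapy: "CBC with differential, bilirubin, ALT (SGPT) and serum creatinine".
- A recheck outside eligibility limits bars protocol therapy.

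Section 10.1(g) carries the same four tests into the removal criteria: "Repeated eligibility laboratory studies (CBC with differential, bilirubin, ALT (SGPT) or serum creatinine) are outside the parameters required for eligibility".

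The limits themselves are in 4.1.5. For liver function, 4.1.5.2 limits bilirubin and ALT and also requires "aspartate aminotransferase (AST) $\leq 2.5 \times$ ULN". Under "Adequate Coagulation Defined As", 4.1.5.5 requires an INR of at most 1.5. On the scale, 4.1.5.2 says "For the purpose of this study, the ULN for SGPT is 45 U/L" and gives no figure for AST. Appendix III states that "the ULN for SGOT is 50 U/L regardless of baseline", and 5.6.1.1 uses the same value.

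AST is measured and read before every pevonedistat dose (6.2.1, 6.3.5, and footnote 8 of the 8.1 table). INR appears neither in that table nor in the delivery maps of Appendix VIII.

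**The concern.** The trigger for the recheck is general, but its content is not. An out-of-limit AST or INR after enrollment sets the recheck off, yet the repeat panel leaves out the test that failed. Treatment is barred only when the recheck fails, so four acceptable results elsewhere clear the patient under the written rule.

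This is an eligibility safeguard that does not do its own job. Section 4.0 says the criteria are read literally and are not waived, so sites should not be left to infer that two unlisted tests belong on the list. Liver enzymes are also an expected toxicity of this agent and part of the DLT definition, so the Day 1 state of AST should be governed by a clear rule. By contrast, 5.3 does name AST among the conditions for starting Cycle 2.

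**Working it through.** The documents give no figure to reproduce. The check compares lists and then locates the AST gap.

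**Step 1: limits against recheck.**

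| Laboratory limit in 4.1.5 | Recheck (4.0, 8.1) | 10.1(g) |
|---|---|---|
| Creatinine (4.1.5.1) | yes | yes |
| Bilirubin (4.1.5.2) | yes | yes |
| ALT (4.1.5.2) | yes | yes |
| AST (4.1.5.2) | no | no |
| INR (4.1.5.5) | no | no |
| Hemoglobin (4.1.5.6) | yes, in the CBC | yes, in the CBC |

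The two omissions are AST and INR, and they are the same in all three places.

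**Step 2: can the age trigger be reached?** Eligibility tests may be done up to 7 days before enrollment (4.0), and therapy may start up to 5 calendar days after it (3.9). The oldest value at start is 7 + 5 = 12 days, which is more than 7, so the trigger can occur within the permitted windows.

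**Step 3: the AST gap on the study scale.** With ULN 50 U/L (5.6.1.1, Appendix III):

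- Entry limit: 2.5 x 50 = 125 U/L.
- Appendix III grades: Grade 1 up to 150, Grade 2 from 151 to 250, Grade 3 from 251 U/L.
- Hold rules: 6.3.5 acts at Grade 3 or higher. The first rule in 6.2.1 is worded as above Grade 3. Neither refers to the entry limit.

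In whole units, 126 to 250 U/L is therefore above the entry limit and below the hold threshold. As an illustration, take a post-enrollment AST of 200 U/L with ALT at or below 2.5 x 45 = 112.5 U/L and the other listed tests within limits. The recheck is triggered, every listed test passes, nothing bars the start, and Grade 2 AST triggers no hold.

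**Step 4: sensitivity to the entry ULN.** Section 4.1.5.2 does not state the AST ULN. If a site used its own (an assumption, since the documents give no local values):

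| Assumed ULN (U/L) | Entry limit, 2.5 x ULN (U/L) |
|---|---|
| 35 | 87.5 |
| 40 | 100 |
| 50 (study value) | 125 |
| 60 | 150 |
| 80 | 200 |

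The uncaught band runs from the entry limit up to 250 U/L, so it is wider with a lower ULN and narrower with a higher one. Only above an assumed ULN of 60 could a patient be eligible while already at study Grade 2.

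**Step 5: INR.** No pre-dose reading or hold rule applies to INR. Any value above 1.5 arising after screening is outside the recheck, 10.1(g) and the schedule.

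**The case against.** The strongest reply is that the 7-day sentence already covers the matter. It is mandatory and has no exceptions, so a stale AST or INR must be renewed, and the four tests can be seen as an additional 48-hour check. For stale values this stands in principle. It does not help a value that worsens within the 7 days, and it does not say what follows when a renewed AST or INR fails.

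The same four tests appear in three places, which may mean that the subset was deliberate. No reason is given, however, and the trigger is not confined to those four tests. The pre-dose AST reading is a real safeguard and makes AST less exposed than INR. Removal on the physician's judgment under 10.1(f) is available, but it is discretion and not a rule on these tests.

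A reader might also infer four stronger points, which the documents do not support.

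- **Spurious DLTs.** One might argue that a raised baseline AST will produce DLTs and so distort the dose decision. A DLT must be Grade 3 or higher and at least possibly attributable to therapy. Although the 5.6.1.1 exception requires return to Grade 1 or lower, 6.2.1 and 6.3.5 accept return to baseline. In the adult azacitidine combination study, the three patients with transaminase DLTs had both AST and ALT raised, and ALT is on the list. No frequency can be derived.
- **Lumbar-puncture risk.** The first intrathecal dose may be given up to a week before Day 1, even before enrollment, and the further doses for CNS2/3 patients begin on Day 8. A recheck within 48 hours before therapy fits neither well.
- **Conflicting AST scales.** Section 5.6.1.1 and Appendix III set 50 U/L for the purposes of the study, which supports using it at entry. Leaving it out of 4.1.5.2 is mostly a drafting gap.
- **INR never measured.** Section 4.1.5.5 requires it for eligibility, and the delivery maps say they list only evaluations needed for the primary and secondary aims. Absence from the schedule does not show that the screening test is skipped.

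**Conclusion.** The point holds in a limited form. The recheck in 4.0 and 8.1, and rule 10.1(g), do not match the laboratory limits in 4.1.5. AST or INR can leave its limits after screening without any written eligibility rule barring the start.

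For AST the gap is about 126 to 250 U/L, assuming the study ULN of 50 U/L applies at entry. For INR it is any value above 1.5, with no second safeguard. How often either would occur cannot be estimated from the documents. The sample size and the dose-decision rule are unaffected. This is an inconsistency that should be corrected because the correction is specific and cheap. It is not evidence that the DLT assessment is biased.

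**What to change.** Reconcile the recheck list in 4.0 and 8.1, and the matching list in 10.1(g), with the laboratory limits already stated in 4.1.5.2 and 4.1.5.5. If the four-test subset is intended, the protocol should say so and explain how an out-of-limit AST or INR is handled. That handling is for the sponsor to settle; the point here is that the passages must agree. Show the INR that eligibility already requires in the pre-study column of the 8.1 table and in the Cycle 1 delivery map. State in 4.1.5.2 whether the AST ULN of 50 U/L from 5.6.1.1 and Appendix III applies at entry.

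The cost is amendment wording and one added tube for INR at an existing draw. AST is already drawn before each pevonedistat dose. The downside is that an occasional enrolled patient will be found ineligible before dosing.

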4.1 Inclusion Criteria

4.1.1 Age: Patients must be ≥ 1 months and ≤ 21 years of age at the time of study enrollment.

4.1.2 Diagnosis:

4.1.2.1 Patients must have had histologic verification of AML at the original diagnosis. Patients must have one of the following:

a) Recurrent disease in $\geq 1^{\text{st}}$ relapse with $\geq 5\%$ blasts in the bone marrow (M2/M3) marrow OR immunophenotypic evidence of disease with $\geq 0.1\%$ blasts detected by flow cytometry, OR evidence of recurrent cytogenetic or molecular abnormalities consistent with relapse, with or without extramedullary disease.

b) Refractory AML is defined as $\geq 5\%$ blasts in the bone marrow (M2/M3) after ≥ 2 induction attempts (i.e., 2 cycles of chemotherapy).

4.1.2.2 Patients with advanced MDS, including MDS that has progressed to AML, and have experienced relapse or are refractory after ≥ 1 course of induction therapy, are eligible.

4.1.3 Performance Level: Karnofsky $\geq 50\%$ for patients > 16 years of age and Lansky ≥ 50 for patients ≤ 16 years of age (See [Appendix I](#)).

4.1.4 Prior Therapy:

4.1.4.1 Patients must have fully recovered from the acute toxic effects of all prior anti-cancer therapy and must meet the following minimum duration from prior anti-cancer directed therapy prior to enrollment. If after the required timeframe, the numerical eligibility criteria are met, e.g., blood count criteria, the patient is considered to have recovered adequately.

a. Cytotoxic chemotherapy or other anti-cancer agents known to be myelosuppressive. See DVL homepage for commercial and Phase 1 investigational agent classifications. For agents not listed, the duration of this interval must be discussed with the study chair and the study-assigned Research Coordinator prior to enrollment.

• ≥ 14 days must have elapsed after the completion of other cytotoxic therapy, with the exception of hydroxyurea, for patients not receiving standard maintenance therapy. Additionally, patients must have recovered from all acute toxic effects of prior therapy.

NOTE: Cytoreduction with hydroxyurea must be discontinued ≥ 24 hours prior to the start of protocol therapy.

b. Anti-cancer agents not known to be myelosuppressive (e.g. not associated with reduced platelet or ANC counts): ≥ 7 days after the last dose of agent. See DVL homepage for commercial and Phase 1 investigational agent classifications. For agents not listed, the duration

THIS PROTOCOL IS FOR RESEARCH PURPOSES ONLY, SEE PAGE 1 FOR USAGE POLICY

of this interval must be discussed with the study chair and the study-assigned Research Coordinator prior to enrollment.

- c. Antibodies: ≥ 21 days must have elapsed from infusion of last dose of antibody, and toxicity related to prior antibody therapy must be recovered to Grade ≤ 1 .
- d. Hematopoietic growth factors: ≥ 14 days after the last dose of a long-acting growth factor (e.g. pegfilgrastim) or 7 days for short-acting growth factor. For agents that have known adverse events occurring beyond 7 days after administration, this period must be extended beyond the time during which adverse events are known to occur. The duration of this interval must be discussed with the study chair and the study-assigned Research Coordinator.
- e. Interleukins, Interferons and Cytokines (other than Hematopoietic Growth Factors): ≥ 21 days after the completion of interleukins, interferon or cytokines (other than Hematopoietic Growth Factors)
- f. Stem cell Infusions (with or without TBI):
 - Allogeneic (non-autologous) bone marrow or stem cell transplant, or any stem cell infusion including DLI or boost infusion: ≥ 84 days after infusion and no evidence of GVHD.
 - Autologous stem cell infusion including boost infusion: ≥ 42 days.
- g. Cellular Therapy: ≥ 30 days after the completion of any type of cellular therapy (e.g. modified T cells, NK cells, dendritic cells, etc.)
- h. XRT/External Beam Irradiation including Protons: ≥ 14 days after local XRT; ≥ 42 days after TBI, craniospinal XRT or if radiation to $\geq 50\%$ of the pelvis; ≥ 42 days if other substantial BM radiation.
- i. Radiopharmaceutical therapy (e.g., radiolabeled antibody, 131I-MIBG): ≥ 42 days after systemically administered radiopharmaceutical therapy.
- j. Patients must not have received prior exposure to MLN4924 (pevonedistat).

